Specific Aim. Assess the cost-effectiveness of the empirically-based incentive intervention for undetectable viral loads. We will assess incremental cost-effectiveness ratio (ICER) by dividing the difference in costs of two interventions by the difference in effects of the two interventions during the 2-year intervention evaluation period on viral load suppression (see below). The ICER can be interpreted as dollars spent per unit of desired outcomes gained. The Incentive Intervention should yield a better ICER.

Specific Aim. Assess the cost-benefit of empirically-based incentive intervention for undetectable viral loads. We will perform a Cost-Benefit Analysis (CBA) to examine the monetized benefits relative to costs for the Usual Care Control and Incentive intervention conditions. The economic outcomes are health care utilization during the 2-year intervention evaluation period (see below). We expect that the Incentive Intervention will yield greater economic benefits relative to its costs than the Usual Care Control.

Measures assessed repeatedly over time will be analyzed with a longitudinal logistic regression model. Within-person correlated outcomes will be handled using generalized estimating equations (GEE; Zeger, Liang, & Albert, 1988). Measures assessed once will be analyzed using logistic regression. The magnitude of effects will be expressed using odds ratios with 95% CI. Intent-to-treat analyses will be adjusted for covariates used for stratification (Pocock et al., 2002). Two-sided tests with p-values <.05 will be considered significant.

- b. Statistical plan including sample size justification and interim data analysis.

STATISTICAL ANALYSES

Measures assessed repeatedly over time will be analyzed with a longitudinal logistic regression model. Within-person correlated outcomes will be handled using generalized estimating equations (GEE; Zeger, Liang, & Albert, 1988). Measures assessed once will be analyzed using logistic regression. The magnitude of effects will be expressed using odds ratios with 95% CI. Intent-to-treat analyses will be adjusted for covariates used for stratification (Pocock et al., 2002). Two-sided tests with p-values <.05 will be considered significant.

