Primary outcome analyses. We will fit a longitudinal logistic regression model $\text{logit}(Y_{ij}) = \beta_0 + \beta_1 tx + \beta_{2-6}x_{2-6} + \epsilon_{ij}$, where Y_{ij} is the presence of a detectable viral load for the i th person at the j th timepoint (8 visits over two years of treatment), β_1 is the covariate of interest representing the expected decrease in log odds of a detectable viral load as a function of assignment to the treatment group, and β_{2-6} are the coefficients for the 5 randomization covariates. Additional models with time and time by treatment interactions will be fit secondarily to assess time trends in treatment effect.

Secondary outcome analyses. We will fit analogous longitudinal logistic regression models for HRMS-verified ART adherence, self-reported adherence, prescription maintenance, and attendance at HIV medical care visits. We will assess post-treatment effects by fitting analogous models for each outcome, but using only data from the two post-treatment visits.

Moderator analyses. For the primary outcome, we will fit models with interactions between treatment and each of the 5 randomization covariates (drug dependence, alcohol dependence, TOFHLA total score, delay discounting, and Beck Depression score) to assess whether treatment effect varies as a function of the putative moderator. For example, for CIDI drug dependence, we would fit the model $\text{logit}(Y_{ij}) = \beta_0 + \beta_1 tx + \beta_{2-6}x_{2-6} + \beta_7 tx * \text{drug dependence} + \epsilon_{ij}$, where β_1 would represent the treatment effect (expressed as a difference in log odds of a detectable viral load between treatment and control groups) among individuals without drug dependence, and β_7 would represent the difference in treatment effect between individuals with and without drug dependence. All moderator analyses will be considered exploratory and will not be corrected for multiple comparisons. These variables will be examined as potential moderators because drug use (Mimiaga et al., 2013), health literacy (Kalichman et al., 2008),

and depression (Murphy et al. 2013) has each been associated with poor adherence to antiretroviral medications. Impulsivity will be assessed as a potential moderator because high levels of impulsivity have been associated with poor health decision making and adverse health behaviors (Axon et al., 2009; Bickel et al. 2014; Bradford et al., 2010).

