Mediation analysis. We will assess potential mediating effects of medication adherence as assessed by qualitative blood testing on viral load using the method of Baron and Kenny (1986). Specifically, this involves estimation of (1) the effect of treatment assignment (incentives) on undetectable viral load without controlling for medication adherence, (2) the direct effect of incentives on medication adherence, and if these two steps yield clinically and statistically significant effects, 3) the effect of incentives on viral load after controlling for medication adherence ($\text{logit } (Y_{ij}) = \beta_0 + \beta_1 x_i + \beta_{2-6} x_{2-6} + \beta_7 \text{adherence} + \epsilon_{ij}$). If medication adherence does mediate the effect of the incentives on presence of a detectable viral load, in this final model we would expect the effect of treatment (β_1) to be attenuated relative to the step 1 model, and for adherence (β_7) to be a clinically and statistically significant predictor of presence of a detectable viral load.

Missing data. We expect to collect $\geq 80\%$ of 3-month assessments (see below). Our primary approach will be to impute all missing values as the adverse outcome (e.g., detectable viral load). Model parameter estimates from this approach will be compared to a method without imputation. If these methods yield differing results, conclusions will need to be tentative. To investigate sensitivity to missing values, participants with and without missing values will be compared by covariates and treatment assignment.

ECONOMIC ANALYSES

We will use the provider perspective using a modified SASCAP and the research team's financial records. Intervention activities will be captured with the modified Economic Form 90 AIR/ED.

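### The plan's one alternative to missing = detectable is an unspecified unimputed analysis, read as an unweighted GEE, that uses no earlier viral load, so a gap between the two estimates cannot show which is off

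*Combined protocol and SAP*

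**What the plan says.** Under Missing data, Section 7b makes missing = detectable the primary rule. It then gives one further estimate: "Model parameter estimates from this approach will be compared to a method without imputation". The response to a discrepancy is: "If these methods yield differing results, conclusions will need to be tentative". As a further look at missingness, "participants with and without missing values will be compared by covariates and treatment assignment". That last comparison gives no treatment effect and does not name earlier viral load.

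The unimputed method is not described there. Section 7b (Statistical analyses) names GEE for all repeated measures, without a working correlation or weights. Under Primary outcome analyses, the model holds treatment plus five terms that "are the coefficients for the 5 randomization covariates". On time, "Additional models with time and time by treatment interactions will be fit secondarily". The natural reading is therefore the same GEE fitted to observed visits. No multiple imputation, weighted GEE, mixed model or tipping-point analysis is planned.

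**The concern.** An unweighted GEE on observed visits is generally valid only if, given the model covariates, the chance of a missing value does not depend on earlier outcomes. In this trial such dependence is plausible and could differ by arm:

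- Incentive participants have paid weekly calls and frequent blood draws, and a failed or missed test resets their payment and schedule (Section 4a, Incentive Group). Controls have no equivalent.
- Viral loads may be taken from clinic records (Risks, item a; COVID-19 Procedures in Section 4a). Being observed can then depend on attending care, which Section 7 expects the intervention to increase.

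At stake is the robustness check on the primary result. If either estimate can be the faulty one, and no third estimate uses the viral load history, a discrepancy leaves the reader with no way to interpret it.

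**Working it through.** **Inputs from the documents.** Eight 3-monthly assessments; 200 randomized; 20% missing; a 15-point difference; 80% power; two-sided 5% (Section 7). All participants are detectable at entry (Section 5).

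**Assumed inputs.** Suppression of 40% v 55%, mean within-person correlation about 0.5, and the missingness rates below. The five covariates were left out of the simulation.

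**The plan's own figure.** 200 × 0.80 = 160, which reproduces. The required N depends on a correlation ρ that cannot be read from the text. With N = 2(1.96 + 0.84)²[p0q0 + p1q1][1 + 7ρ]/(8 × 0.15²), the worst case gives N = 162 at ρ = 0.40 and 192 at ρ = 0.50. A worst-case N of 150–160 would imply ρ of about 0.36–0.39.

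**Step 1: the imputed estimate under random missingness.** The complete-data odds ratio (OR) is (0.55/0.45)/(0.40/0.60) = 1.83. With 20% missing completely at random and set to detectable, the rates become 0.55 × 0.80 = 0.44 and 0.40 × 0.80 = 0.32. The OR is then (0.44/0.56)/(0.32/0.68) = 1.67, and the difference falls from 15 to 12 points. The observed-visit estimate is unaffected.

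**Step 2: the observed-visit estimate under outcome-linked missingness.** With independence, each arm contributes its pooled observed proportion. In the limiting case where status never changes within a person, observed odds = true odds × (chance observed if suppressed)/(chance observed if detectable). This gives bounds:

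- Same rule in both arms (10% missed after suppressed, 28% after detectable): both odds are multiplied by 0.90/0.72, so the OR stays at 1.83.
- Rule mainly in control (10%/35%; Incentive 15% throughout): 1.83/(0.90/0.65) = 1.32.
- Rule mainly in Incentive (5%/40%; control 15% throughout): 1.83 × (0.95/0.60) = 2.90.

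With no persistence the OR stays at 1.83, so real data fall in between.

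**Step 3: large-sample simulation** (4,000–6,000 per arm). The complete-data OR in this draw was 1.77, so compare within rows.

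| Missed after suppressed/detectable | Complete | Missing = detectable | Observed, independence | Observed, exchangeable | Weighted on last result |
|---|---|---|---|---|---|
| (a) 10/28, both arms | 1.77 | 1.68 | 1.78 | – | – |
| (b) control 10/35, Incentive 15/15 | 1.77 | 1.73 | 1.50 | 1.71 | 1.76 |
| (c) control 15/15, Incentive 5/40 | 1.77 | 1.64 | 2.24 | 1.84 | 1.78 |
| (d) 20% at random | 1.77 | 1.60 | 1.75 | – | – |

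(– = not listed for this draw.) In companion runs with the (b) and (c) rules, missingness averaged over arms was 20–22%, close to the plan's 20%. For example, (0.27 + 0.15)/2 = 0.21 for (b).

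A separate simulation with complete-data OR about 1.85 gave 1.65–1.66 or 2.06–2.08 under independence, 1.79–1.90 under exchangeable correlation, and 1.83–1.86 with weighting.

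**Step 4: trial size** (100 per arm, 1,500 replicates, independence). The two planned analyses disagree on significance in 5–6% of trials under (a) and (d), 32% under (b) and 23% under (c). With no true effect, the observed-visit test rejects in 11.5% (b) and 16.8% (c) of trials. The imputed analysis rejects in 6.7% and 4.8%.

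**Step 5: missingness that depends on the unseen result.** In a setting with rising suppression and complete-data OR 1.77, where control missed visits were mostly suppressed ones, the imputed OR was 2.23. The observed-visit OR was 2.10 (independence) or 1.97 (exchangeable). Both planned methods are then too high.

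**The case against.** The case against is substantial. The comparator is not named, so calling it an unweighted GEE is an inference. Both arms are paid $100 per follow-up assessment (Section 9a), and record-based viral loads mean that a missed visit need not be a missing value. Missingness may therefore be modest and similar by arm, in which case little is gained. A named exchangeable correlation removes most of the bias. In a further simulation with a true 15-point difference, independence gave 11.5–13.9 points and exchangeable GEE 14.2–14.8, although that simulation's correlation structure favoured the exchangeable estimator. If ρ is nearer 0.36–0.39 than 0.5, the independence bias should also be smaller than shown. Tentative conclusions are a defensible response to disagreement. All of this stands and limits the size of the point. It does not remove it: the working correlation is not stated, and no planned estimate uses earlier results.

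Four stronger readings are tempting, and the documents do not support them:

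- *That this is the only check on missing data.* Section 7b also plans a descriptive comparison by covariates and arm. The unimputed analysis is the only alternative effect estimate.
- *That the missing visit term causes the bias.* Adding it moved the OR by at most 0.08 (1.50 with and without it in scenario b), and models with time are planned secondarily.
- *That the two methods err in opposite directions.* In scenario (b) both fall below the complete-data value (1.73 and 1.50 against 1.77).
- *That an imputed or weighted estimate should decide.* It assumes that missingness depends only on observed data, which cannot be tested here.

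**Conclusion.** The point holds as a conditional weakness of the sensitivity analysis. The choice of missing = detectable as primary is not in question. If missed visits follow a detectable result to a different degree by arm, an independence GEE on observed visits is biased (OR 1.50 or 2.24 against 1.77; 11.5–16.8% false rejections at a nominal 5%). The bias is smaller with exchangeable correlation (1.71 or 1.84) and close to nil when both arms follow the same rule. The imputed estimate is itself off in some settings, including purely random missingness. A gap between the two planned estimates therefore does not show which is wrong. The sizes rest on assumed missingness rates, suppression levels and within-person correlation; the documents give only 20% missing and a 15-point difference.

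**What to change.** In Section 7b (Missing data):

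- State that the unimputed comparator is the primary GEE fitted to observed visits with an exchangeable working correlation.
- Add one prespecified sensitivity analysis that uses earlier results. It can be multiple imputation within arm from intake viral load, all earlier viral loads and the five randomization covariates, or GEE weighted by the inverse probability of being observed.
- Report it beside the two planned estimates and say in advance that it helps interpret disagreement but does not override the primary.
- An arm-specific tipping-point analysis can cover missingness that depends on unobserved results.

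This is a cheap improvement. Intake and 3-monthly viral loads are already scheduled, so the cost is SAP wording and one or two more models to program and report. The imputed or weighted analysis still assumes that missingness depends only on observed data.

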Participants (N = 200) who complete the HIV Medical Care Education program will be randomly assigned to a Usual Care Control group or the Incentive group. A computerized urn randomization procedure (Wei & Lachin, 1988) will be used to balance groups on five baseline characteristics that may influence outcome: (1) opiate or cocaine positive urine sample at intake to the study (Y/N); (2) Self-reported use alcohol to intoxication on 20 or more days in the past 30 on the ASI (Y/N); (3) health literacy as assessed on the TOFHLA (score \leq the rolling median, Y/N); (4) impulsivity as assessed by delay discounting (k value from the raw discounting data for each participant, which is an index of impulsivity (\leq the rolling median of k, Y/N); and (5) depression as assessed by the Beck Depression Inventory (score \leq the rolling median, Y/N). Participants will be stratified by DSM V cocaine, opiate and alcohol dependence, health literacy, and depression at intake because drug use (Mimiaga et al., 2013), health literacy (Kalichman et al., 2008), and depression (Murphy et al. 2013) has each been associated with poor ART adherence. Participants will be stratified based on measures of impulsivity because high levels of impulsivity have been associated with poor health decision making and adverse health behaviors (Axon et al. 2009; Bickel et al. 2014; Bradford et al., 2010). Participants will be taught the details of their group with written instructions and quizzes. Participants will earn up to about \$15 for answering questions on the quiz.

Incentive Group

The Incentive group will receive the novel empirically-based incentive intervention to promote long term suppression of HIV-1 RNA (viral load) being evaluated in this study. The incentive intervention will employ features and parameters that have been shown critically important to promote therapeutic behavior change in drug users and other populations (Higgins et al., 2008; Lussier et al., 2006; [name] et al., 2011). Participants will be taught the details of the incentive program with written instructions and quizzes.

A Prescription for ART. When a participant gets assigned to the Incentive group, he/she will be asked if he/she has a current prescription for ART and if he/she has at least a 2-day supply of medication. As described below, blood draws and the incentive program described below will not begin until the participant has an active ART prescription and has at least a 2-day supply of medication.

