Intake Only Assessment Instruments. At intake we will administer: 1) BDI to screen for depression (Beck et al. 1993). 2) Test of Functional Health Literacy in Adults (TOFHLA) to measure health literacy (Parker et al., 1995). 3) A computer delay discounting task to assess impulsivity (Johnson and Bickel, 2002). In this task, on each trial the participant makes a choice between a smaller immediate reward option (e.g., \$5 now) and a larger \$10 reward delivered after a given delay (e.g., 1 week). The magnitude of the smaller immediate reward is adjusted across trials to determine an indifference point, or the amount of immediate money equal to the delayed \$10. Once an indifference point is detected, the task moves to the next of four delays (1 day, 1 week, 1 month, 6 months); 4) The Addiction Severity Index; 5) The Wide Range Achievement Test.

Intake, 3-Month and 6-month Follow-up Assessments. We may conduct these assessments at all time points: 1) HIV-1 RNA (viral load) in blood by Maryland DHMH Laboratories. 2) The presence or absence of 15 ART medications in blood (Marzinke et al., 2014). 3) We may assess blood samples that we collect for the quantitative levels of antiretroviral medications or their metabolites to determine if participants are maintaining the presumed therapeutic blood levels of the antiretroviral medications. The assessments of quantitative blood levels of antiretroviral medications could provide more information than the qualitative tests. For example, a participant could test positive for an antiretroviral medication on the qualitative test by taking the medication occasionally, but not take the antiretroviral medication often enough to maintain therapeutic blood levels of the medications. 4) blood tests of CD4 counts; 5) urine tests of drugs of abuse. 6) A

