visual analog scale (VAS) to assess ART adherence in which participants mark a 100 mm line to indicate their percent adherence to their antiretroviral medications over the previous 4 weeks (Buscher et al., 2011; Walsh et al., 2002). Responses on this VAS have been associated with pill taking with MEMS (Buscher et al., 2011; Walsh et al., 2002), pill count (Walsh et al., 2002), and pharmacy records (Buscher et al., 2011). 7) Assess whether each participant refilled their ART prescription for each month, the pharmacy that filled each prescription, and the medication. 8) Pharmacy records will be obtained (with participant permission) to confirm self-reported data. 9) Participants will be asked how many primary HIV care visits they had in the past 3 months using procedures and definitions used in a prior multisite study (Purcell et al., 2007). Medical records will be obtained with permission to confirm self-reports. 10) The *Modified Economic Form 90 AIR/ED* will be created for this study based on the Economic Form 90 AIR/ED (Bray et al., 2007; Miller and Del Boca, 1994; Scheurich et al., 2005; Tonigan et al., 1997) to collect patient data on all health care utilization within the past 180 days. 10) A Modified SASCAP (Zarkin, Dunlap et al. 2004) will be used to estimate the costs associated with services in the study conditions. The SASCAP (www.rti.org/sascap) assesses activity-level resource use and cost data for intervention staff, consultants, and non-labor resources (e.g., building space) used in the provision of intervention services. The SASCAP method reliably estimates the costs of intervention activities and the cost per participant. Zarkin and Dunlap have applied this micro-costing approach (Zarkin et al., 2003, 2005, 2008, 2010; Dunlap et al., 2010). 11) A multiple-choice test evaluating the HIV Education Course.

b. Study duration and number of study visits required of research participants.

Participants in the incentive group will receive the incentive intervention for two years. For all participants, assessments will be conducted at intake to determine eligibility and characterize participants. Outcome assessments will be conducted at intake, every 3 months throughout the 2-year intervention evaluation and every 6 months of the 1-year follow-up period.

c. Blinding, including justification for blinding or not blinding the trial, if applicable.

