Cost Analysis. We will derive cost estimates following an activity-based approach (Drummond et al., 2005; Gold et al., 1996; Zarkin, Dunlap et al., 2004; Zarkin et al. 2005 Zarkin, Dunlap, et al., 2008; Dunlap et al., 2010). The total cost per participant of each intervention (HIV health care costs and incentive/feedback program costs) will be the sum of the costs of (1) staff labor, (2) incentive payments; (3) medication; (4) building space, and (5) other supplies or materials. The labor costs of each activity are equal to the product of the amount of time spent by each person on the activity and their hourly wage. We will multiply the unit cost of other intervention resources with the quantity used per activity. The total intervention cost for each participant is the cost per activity multiplied by the number of activities received by the participant. The mean across patients in a given intervention condition yields the intervention's mean per participant cost.

[figure not shown]
Cost-Effectiveness (CEA). Our CEA methodology follows a standard economic approach (Drummond et al., 2005; Dunlap, Zarkin, et al., 2010; Siegel et al., 1996; Zarkin et al., 1996, 1997, 2008). The primary cost-effectiveness outcomes will be the percentage of participants with undetected viral loads at 24 months (end of intervention) and at 36 months (post-intervention). The incremental cost-effectiveness ratio (ICER) is calculated by dividing the difference in costs of two alternatives by the difference in their effects of the two alternatives. The estimated ICER can be interpreted as dollars spent per unit of desired outcomes gained (e.g., \$900 per percentage point increase in participants with undetected viral loads). To gauge the sampling uncertainty of the ICERs, we will calculate confidence intervals via nonparametric bootstrap methods (Indurkha et al., 2001; Briggs et al., 2006). We will estimate cost-effectiveness acceptability curves (CEACs) using nonparametric bootstrap methods (Dunlap et al., 2008, 2010; Fenwick et al., 2001, 2006). The CEACs incorporate the inherent variability of the cost and effectiveness estimates and show the probability that a treatment is cost-effective as a function of the policy maker's intrinsic valuation or willingness to pay for the clinical outcome.

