Cost-Benefit (CBA). We will examine the monetized health care benefits relative to costs for the two intervention conditions. Because previous studies have shown that health care costs can be much higher in individuals with higher viral loads (e.g., Chen et al., 2006; Gebo et al., 2010), primarily due to higher non-antiretroviral medications and hospitalizations, we will focus on assessing and monetizing the potential differences in health care utilization during the 2-year intervention period for the incentive condition group relative to the usual care group. Health care utilization will be collected using the modified Economic Form 90 AIR/ED. Unit costs used in monetizing these economic outcomes will be drawn from literature and public data.

Sensitivity Analysis. We will conduct sensitivity analyses to assess whether the economic results are affected by changes in model parameters, such as assumptions made in estimating costs. We will perform one-way sensitivity analyses and examine the effect of changing one of the model parameters holding all other parameters constant, as well as n -way sensitivity analyses in which n parameters of the model are varied jointly.

POWER ANALYSIS

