The primary outcome measure of undetectable viral loads will be analyzed with a longitudinal logistic regression model using GEE (Diggle & Diggle, 2002). We used Liu and Liang (1997) to determine the total N required to detect a difference between groups with 80% power. The adjacent figure shows the total number of participants (N) required to detect a difference of 15% between the Usual Care Control and the Incentive Group at the eight 3-month assessments during the intervention evaluation period. The figure shows different percentages for the Usual Care Control group because that value affects the sample size required. 15% is smaller than the effects produced in all prior studies of voucher reinforcement of cocaine or opiate abstinence or medication adherence and smaller than all effects produced by the Therapeutic Workplace and smaller than the incentive effects in promoting drug abstinence, medication adherence and other health behaviors as shown in three different meta-analyses (Petry et al., 2012; Prendergast et al. 2006; Lussier et al., 2006). The horizontal red lines show the number of participants planned based on the number of participants enrolled and randomized to the two groups without (top dashed line) and after adjusting for the anticipated rates of missing data (20% missing, bottom solid red line). Based on this analysis, we need to enroll and randomize 200 participants (horizontal dashed line) to ensure that we have sufficient sample sizes after adjusting for the rates of missing data. After adjusting for missing data (20% missing), this would yield a sample size of 160 participants (200 participants x 0.80 collected samples = 160 participants). The adjusted sample size of 160 participants (solid red line) is a little more than the maximum number of participants that would be required.

c. Early stopping rules.

The protocol can be stopped based on recommendations of the Scientific Advisory Committee overseeing this study. We will ask the Scientific Advisory Committee to recommend that the trial be stopped if a review of the adverse events suggests to any of the investigators that the number of related and unexpected adverse events is unacceptably high. The Scientific Advisory Committee will be allowed to request statistical analyses to compare the groups on the rates of different adverse events or to have the adverse event data summarized in other ways that they deem appropriate.

Risks

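### The economic comparisons make no use of health care use before randomisation, so they are unbiased but less precise than they could be

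*Combined protocol and SAP*

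**What the plan says.** **Estimators.** Section 7b, Cost Analysis, builds each participant's cost from labour, incentive payments, medication, space and supplies, then averages within arm: "The mean across patients in a given intervention condition yields" the figure used for that arm. The Cost-Effectiveness paragraph divides the cost difference by the effect difference, with nonparametric bootstrap intervals and acceptability curves (CEACs). The Cost-Benefit paragraph will monetise "differences in health care utilization during the 2-year intervention period"; it writes out no estimator and no method for uncertainty. The economic sensitivity analyses vary model parameters. None of these uses a baseline value.

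**Baseline measure.** Section 4a, Assessments, describes the modified Economic Form 90 as designed "to collect patient data on all health care utilization within the past 180 days". It stands in the list for intake, 3-month and 6-month assessments, which opens "We may conduct these assessments at all time points". The same form supplies the CBA outcome.

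**Balance and adjustment.** The urn randomisation (Section 4a, Experimental Design) uses drug-positive urine, alcohol use, health literacy, impulsivity and depression. The adjustment sentence in Section 7 follows the logistic and GEE models and covers only the stratification covariates. Even if it is read to include the economic aims, prior health care use stays out.

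**The concern.** At intake, the 180-day window of the Form 90 falls before randomisation. The value therefore cannot be affected by the incentives, and it is a natural predictor of later use. The plan foresees the measure but gives it no analytic role.

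The Cost-Benefit paragraph attributes higher costs at higher viral loads mainly to hospitalisations and non-antiretroviral medication. Such costs are typically skewed, so a few heavy users at intake can move the mean of about 100 people.

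Cost, cost-effectiveness and cost-benefit are each a specific aim, and the protocol summary makes wider use of the intervention conditional on its being economically sound. No precision is stated for these aims. At stake are wider intervals than the data require and, for the CBA, a difference that may be reported with no interval at all.

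**Working it through.** **Inputs from the documents.** "Participants (N = 200) who complete the HIV Medical Care Education program will be randomly assigned" to two groups. No allocation ratio is given, so I assume 1:1, or 100 per arm. The Power Analysis aims to "determine the total N required to detect a difference between groups with 80% power" for viral load, with N "required to detect a difference of 15% between the Usual Care Control and the Incentive Group". It states no power or precision for cost. Its one figure relevant here reproduces: 200 × 0.80 = 160, or 80 per arm.

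**Inputs assumed.** The documents give neither the SD of cost nor the correlation r between intake use and later cost. I take r from 0.1 to 0.7 and work in SD units.

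**Formulas**, with n per arm:
- SD of the chance difference in intake use = √(2/n) baseline SD. For n = 100 this is 0.141, with 95% range ±1.96 × 0.141 = ±0.277. For n = 80 it is 0.158 and ±0.310.
- 95% carry-over into the unadjusted cost difference = r × that range, in outcome SD.
- Adjusted SE / unadjusted SE = √(1 − r²).
- Unadjusted N with the same precision = 200 / (1 − r²).

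| r | Carry-over, n = 100 | Carry-over, n = 80 | SE ratio | SE reduction | Equivalent N |
|---|---|---|---|---|---|
| 0.1 | ±0.028 | ±0.031 | 0.995 | 0.5% | 202 |
| 0.3 | ±0.083 | ±0.093 | 0.954 | 5% | 220 |
| 0.5 | ±0.139 | ±0.155 | 0.866 | 13% | 267 |
| 0.7 | ±0.194 | ±0.217 | 0.714 | 29% | 392 |

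**Skewed costs.** I simulated 5,000 trials of 100 per arm at each setting, with no arm effect and lognormal intake and later costs (log SD 1). At log-scale correlations of 0.1, 0.3, 0.5 and 0.7, the raw-scale correlations are 0.06, 0.20, 0.38 and 0.59. The ratio of adjusted to unadjusted SD was 0.999, 0.984, 0.915 and 0.803. Both estimators were centred on zero. Skew lowers the raw-scale correlation, and the gain shrinks with it.

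**In dollars, for illustration only.** Assume a 2-year cost SD of $30,000 and r = 0.5.
- Unadjusted 95% half-width: 1.96 × 30,000 × √(2/100) = $8,316.
- Part due to intake imbalance: 0.5 × 8,316 = $4,158.
- Adjusted half-width: 8,316 × √(1 − 0.25) = $7,202.

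The two parts combine as squares (4,158² + 7,202² ≈ 8,316²). Removing the first therefore narrows the half-width by $1,114, or 13%, and not by $4,158.

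**The case against.** A difference in means with a nonparametric bootstrap is a valid analysis of a randomised comparison. Chance imbalance is ordinary sampling error, and the intervals and CEACs planned for the ICER already contain it. Adjustment is thus an optional gain for secondary aims. All of this stands.

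The gain may also be small. Eligibility admits people who are not receiving HIV care, and Section 7a expects more treatment engagement in the Incentive arm. For HIV care costs, low intake use may mean being out of care and not low later cost, so r could be low. Incentive payments arise in one arm only and depend on viral load results after randomisation, so prior use probably predicts them poorly. These points stand too, and they place the main benefit in the CBA. The Cost Analysis does, however, include HIV health care costs and medication as well.

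A reader might infer that imbalance in prior use passes undiminished into incremental cost and would be taken for an effect of the incentives, by an amount close to the programme's own cost. The documents do not support this. Carry-over is scaled by r and is not bias. Plain arm averages are explicit for cost and implied for the ICER, but the CBA names no estimator. The largest payout for incentives and weekly calls is 730 × $10 + 104 × $5 = $7,820. Carry-over reaches that order only at the corner of an assumed range: ±$7,761 at SD $40,000 and r = 0.7, against ±$4,158 in the middle and ±$1,663 at SD $20,000 and r = 0.3.

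The objection does not dispose of two things. The bootstrap shows this error for the ICER but does not reduce it, and for the CBA nothing is planned that would show it.

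**Conclusion.** The point holds as a loss of precision. No economic comparison uses intake health care use, although an instrument for it is listed at intake and neither the randomisation nor the stated adjustment covers it. The unadjusted estimates are unbiased.

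The reduction in SE forgone runs from negligible at r = 0.1 to 29% at r = 0.7, and is smaller than these figures where skew weakens the raw-scale correlation. The percentages do not depend on arm size. They rest wholly on an assumed r, and the dollar figures also on an assumed SD, so the documents cannot fix the size. The effect is probably largest for CBA utilisation and smaller for intervention cost. The primary viral load analysis is untouched. The change is worth making because it costs little and because settling it now prevents a choice about adjustment after the results are seen.

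**What to change.** 1. In Section 4a, change *may* to *will* for the Form 90 at intake, for all participants. As worded, the covariate is planned but not guaranteed.
2. In Section 7b, define incremental utilisation (CBA) and incremental cost (ICER) as the arm coefficient, in dollars, from a linear regression of each participant's 2-year monetised value on arm and monetised intake Form 90 value. A gamma model is less suitable: it cannot take zero values, and with a log link its coefficient is a ratio and not the dollar difference that the ICER needs.
3. State a simple rule for a missing intake value, such as mean imputation.
4. Refit the regression in every bootstrap replicate for the ICER and CEAC, and give the CBA difference a bootstrap interval in the same way.
5. Report unadjusted means alongside.

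The cost is plan wording, a firm commitment to a form already listed, and slightly more analysis work. No new visit or instrument is needed. If r proves low, little is gained.
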